6.4.4 Handling of Subjects Unable to Tolerate an MR Scan

In cases where the scan cannot be tolerated by the subject, remove the subject from the scanner. Assess the subject for possible adverse events, and treat the subject's reported symptoms according to your institution's standard of practice. Document the reason for the intolerance. At a minimum, information related to the sequence used to perform the scan, the length of time the subject was scanned, and the whole body SAR level reached should be collected and submitted to St. Jude Medical. A repeat scan is not required to be completed.

6.5 Post-MRI Scan Procedures

Following the MRI Scan, remove the subject from the MRI bore.

6.5.1 Post-MRI Device Programming and Assessment

- 1) Interrogate the subject's device using a Merlin programmer.
- 2) Reprogram device to subject's permanently programmed parameters.

Clinical Investigational Plan

3) Determine the subject's underlying rhythm

- If there is no intrinsic rhythm when the device is programmed to pace at 40 bpm, the subject is considered pacemaker dependent.

4) Obtain the following measurements for all leads, as applicable, with the permanently programmed parameters.

- Remaining battery capacity
- Capture threshold for all leads
- Sensing amplitude for RA and RV leads
- Pacing lead impedance for all leads
- HVLI impedance

NOTE: *RV capture thresholds are not required to be obtained if a high ventricular rate is present (e.g. 110bpm). If available, sites should use the automatically obtained pacing capture threshold from the most recent archival data as a substitute for the in-clinic capture threshold. RV sensing measurements are not required if the subject's intrinsic rate has been established to be ≤40 beats per minute.*

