4.4.2 Additional Data

- Demographics: gender, age, ethnicity, race, cardiac disease history, arrhythmia history, etc.
- A summary of scan location (i.e. head, extremity, and lumbar).
- A summary of clinical findings based on review of MRI scans
- A summary of device electrical measurements at the MRI Scan Visit (before and immediately after the MRI scan) and at Follow-up Visit(s).
- A summary of adverse events (ADE, SADE, UADE)
- A summary of MRI-related complications
- Mortality
- Estimate of the incidence rate of device patients undergoing a clinically indicated MRI.

The above data will be summarized by each main device group (pacemaker/CRT-P and ICD/CRT-D).

Clinical Investigational Plan

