6.5.2 Reporting of MRI Scan-Related Adverse Device Effects

An ADE or SADE related to the following should be reported as soon as possible, but no later than 10 working days, to St. Jude Medical: clotting, pulmonary embolism, or heating of the device pocket during the MRI scan. These events are likely to be associated with symptoms occurring during or immediately following the MRI scan and may manifest as chest pain, shortness of breath, or changes in vital signs during or immediately following the MRI scan.

To ensure all ADEs or SADEs related to or caused by the MRI scan are appropriately captured, before starting the scan, verbally instruct the subject to report symptoms of chest pain, shortness of breath or pocket discomfort that he/she experiences while being scanned or immediately after exiting the scanner. Note changes in vital signs such as changes in heart rate, room air blood oxygen saturation, and/or respiration rate that occur during the MRI scan that may suggest an ADE or SADE has occurred due to clotting, pulmonary embolus or related to lead tip or device pocket heating.

If symptoms during or immediately after the MRI scan suggest that an ADE or SADE has occurred due to clotting, pulmonary embolus or related to lead tip or device pocket heating, test to assess possible causes. Diagnostic testing may be performed in any order deemed appropriate by the investigator; if any test was not performed, provide medical justification for not performing that test:

- (1) A 12-lead EKG
- (2) A 2-view chest X-ray (PA and Lateral).
- (3) Room air blood oxygen saturation
- (4) A transthoracic echocardiogram.

Clinical Investigational Plan

If the subject reports pocket discomfort, ask the subject for additional descriptive information and determine if the pocket is discolored or warm to the touch. EKG, chest x-ray, room air blood oxygen saturation, or transthoracic echocardiogram testing are not required to be performed for symptoms related to device pocket heating.

Sites should report an ADE or SADE if the subject experiences a significant rise in pacing threshold ([contact] or greater) from pre-MRI scan to post-MRI scan.

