6.5.4 Data Submission

Once all the required testing has been performed at this visit, complete and submit the Enrollment and MRI Scan Case Report Forms to St. Jude Medical. If an adverse event or death occurred, submit an Adverse Event, Death Case Report Form, and Product Out of Service Case Report Form, as applicable. Report any deviations or withdrawals by submitting a Deviation or Withdrawal Case Report Form.

Export the MRI scan onto a CD, or other form of electronic media in DICOM format, and send to St. Jude Medical. Upload pre and post MRI scan device session records through the EDC study portal or Merlin.net. It is recommended that the following device printouts and measurements be maintained at the site.

- FastPath Summary
- Test Results with Freezes, Include Battery & Leads
- Wrap-up Overview with full parameters
- Upload device session record

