6.6 Follow-Up Visit Procedures

The subject's scheduled follow-up visits will be based upon the change in the device parameters from the MRI Scan Visit (pre-MRI scan to post-MRI scan measurements).

Clinical Investigational Plan

If the subject had a follow-up visit at another institution, then the follow-up data, including device measurements and pertinent medical records may be obtained per the medical record release authorization statement in the informed consent.

6.6.1 Significant Parameter Changes:

Table 7. List of Significant Parameter Changes Requiring Multiple Follow-Ups

A change in remaining battery capacity of $\geq 2\%$
A change in pacing lead impedance > 50 ohms
A change in high-voltage lead impedance (HVLI) ≥ 7 ohms
Decrease in P wave sense amplitude $\geq 50\%$
Decrease in R wave sense amplitude $\geq 25\%$
Increase in capture threshold $\geq 0.5V$ at the pre-programmed pulse width

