6.6.3 Subjects requiring only a single follow-up visit

Subjects that did not have any of the significant parameters changes shown in Table 7 will be required to return for a single follow-up visit at 1 month (-7/+14 days) after the MRI scan.

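### With a high ventricular rate, section 6.5.1 has sites enter an archived automatic RV capture threshold as the post-MRI value without requiring that it was recorded after the scan

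*Combined protocol and SAP*

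**What the plan says.** Section 6.5.1 of the combined protocol and SAP lists the measurements to take after the scan, among them "Capture threshold for all leads". Table 4 places this check on the day of the scan. The NOTE below the list makes an exception: "RV capture thresholds are not required to be obtained if a high ventricular rate is present (e.g. 110bpm"). It continues: "If available, sites should use the automatically obtained pacing capture threshold from the most recent archival data as a substitute" for the in-clinic value. The same NOTE stands in 6.3.4 (pre-MRI) and 6.6.5 (follow-up). None of the three sets a date or time condition on the archived reading.

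The pre-to-post change has three uses:

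- **Summary.** Sections 4.4.2 and 12.1.3 plan "A summary of device electrical measurements at the MRI Scan Visit (before and immediately after the MRI scan") and at follow-up.
- **Follow-up schedule.** Section 6.6 makes it "based upon the change in the device parameters from the MRI Scan Visit (pre-MRI scan to post-MRI scan measurements"). In Table 7, a capture-threshold increase of at least 0.5 V is one of the changes that lead to two visits. Subjects with none of the listed changes "will be required to return for a single follow-up visit at 1 month" (6.6.3).
- **Event reporting.** Section 6.5.2 says: "Sites should report an ADE or SADE if the subject experiences a significant rise in pacing threshold" between the pre- and post-scan measurements. The cut-off cannot be read in the available text.

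On data checks, 6.5.4 says: "Upload pre and post MRI scan device session records through the EDC study portal or Merlin.net". Section 9.1 provides for a Data Management Plan covering review and queries. Section 12.8 excludes spurious data, without defining the term, and summarizes the reasons for exclusion. The case report forms are held separately (Appendix G).

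**The concern.** A post-scan threshold is useful because it can be compared with the value before the scan. Table 1 names electrode heating with loss of sensing or capture among the potential MRI-related events, so the comparison bears on a risk the protocol itself identifies.

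A site that follows the NOTE exactly can enter, as the post-MRI value, a number the device stored before the subject entered the scanner. A missing value would be visible in the data. A pre-scan value in the post-scan field would not be, and it would tend to read as no change. At stake are the accuracy of one descriptive item and whether a real RV rise is seen at the scan visit by the two rules that depend on it.

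**Working it through.** The plan gives no figure to reproduce here. The check is whether the text permits a pre-scan value and, if so, what the recorded change then measures.

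**Step 1: is a pre-scan value permitted?** The NOTE in 6.5.1 asks for the most recent archived value and says nothing of its date. Sections 4.4.2 and 12.1.3 state the intended timing of the summary but do not restrict the substitute. Sections 6.5.4, 9.1 and 12.8 specify no date check. A pre-scan value is therefore a compliant entry.

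**Step 2: is it likely?** The documents do not say when or how often automatic values are stored. Three facts suggest a short window for a new one: the check is on the scan day, Table 5 recommends pacing off during the scan for subjects with a stable underlying rhythm, and 6.5.1 restores the permanent settings at step 2, shortly before the measurements at step 4. This is inference only and gives no frequency.

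**Step 3: what would the recorded change be?** Let C be an in-clinic pre-MRI value, A an archived value stored before the scan, P a genuine post-scan value, and d the true scan-related change.

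- Intended: P − C, which contains d.
- Case (a), the same archived value used before and after: A − A = 0 V, whatever d is.
- Case (b), in-clinic before and archived pre-scan value after: A − C, a difference of method and time that does not contain d.

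**Step 4: what does the Table 7 item then do?** For one subject, take independent normal reading errors with SD s and no systematic difference between methods. The chance that the recorded change reaches 0.5 V is 1 − Φ((0.5 − δ)/(s√2)), with δ = d for a genuine post-scan reading and δ = 0 in case (b). The documents give no SD, so s is assumed over 0.1 to 0.25 V. For an assumed true rise d = 1.0 V:

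| s (V) | s√2 (V) | 0.5/(s√2) | Genuine post-scan value | Case (b) | Case (a) |
|---|---|---|---|---|---|
| 0.10 | 0.141 | 3.54 | 1.000 | 0.000 | 0 |
| 0.20 | 0.283 | 1.77 | 0.961 | 0.039 | 0 |
| 0.25 | 0.354 | 1.41 | 0.921 | 0.079 | 0 |

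The case (b) figures are the false-positive rate alone and stay the same for any true rise. The table shows what happens within one affected subject. It says nothing about how many there are.

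**The case against.** The strongest case against is that the problem may never occur. It needs a high ventricular rate at the post-scan check, an available archived value, and a value older than the scan. The most recent archived value could be a post-scan one. Case (a) further needs the archived value to have been used before the scan. In 6.3.4 the RV threshold must also be verified for eligibility at step 2, whereas the NOTE follows the later measurement step and does not expressly waive that verification. All of this stands, and it is why no frequency is claimed.

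There are also safeguards. The uploaded session records might show the date, the Data Management Plan might prompt a query, and the case report forms might already record the source. Thresholds on other leads, where present, and the other Table 7 items can still trigger the early visit. Every subject has a 1-month visit with adverse-event evaluation, and 6.5.2 turns on a rise the subject experiences, not only on the entered number. These limit the consequences. They do not clearly catch the entry: no date check is specified, a compliant value is not obviously spurious, and the follow-up NOTE has no date condition either.

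A reader might infer more than the documents support:

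- **That the study will understate the proportion of subjects with an RV rise by some number of percentage points.** The plan reports no such proportion and no confidence bound on it. The 0.5 V figure is a follow-up trigger, and the number affected is not given.
- **That archived values will usually be pre-scan.** The storage schedule is not described.
- **That the main result is biased.** The primary endpoints concern image quality, and sections 12.3 and 12.9 state that there is no pass/fail criterion and no hypothesis.

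**Conclusion.** The concern holds as a conditional one. The NOTE directs sites to a substitute that may be older than the scan, and nothing in the documents prevents it from being recorded as post-MRI. When that happens, the RV change is uninformative about the scan, or zero by construction if the same value was used twice. An RV rise can then be missed in the device-measurement summary, in the capture-threshold item of Table 7 and in threshold-rise reporting.

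The size cannot be stated for any planned statistic: the number of affected subjects is unknown and may be zero. The effect is confined to the RV threshold in subjects with a high ventricular rate. The conclusion rests on the text alone; the SDs and the 1.0 V rise in the illustration are assumptions. Whether a gap remains in practice depends partly on the case report forms and the Data Management Plan, which are not part of the documents. Severity: minor.

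**What to change.** 1. **6.5.1:** accept an archived RV threshold as the post-MRI value only if its time stamp falls after the end of the scan and no later than the post-MRI check.
2. **6.6.5:** accept it only if it was recorded after the scan and within the window of the visit it is entered for. A condition of post-scan timing alone would let a scan-day reading stand as the 1-month value.
3. **6.3.4, 6.5.1 and 6.6.5:** record the source (in-clinic or archived automatic) with date and time. For the scan visit these can be checked against the session records uploaded under 6.5.4. In the summary, flag changes that compare different methods, since a correctly dated archived value set against an in-clinic baseline still mixes methods.
4. **Otherwise:** record the value as missing, exclude it from the change summary, and report the reason and the count under 12.8. Section 12.8 already asks for reasons; the count is an addition.
5. **Follow-up:** the sponsor should reconcile 6.5.1 with 6.6.1 to 6.6.3 on how follow-up is assigned when this value is missing. The question already arises under the current text whenever no archived value is available.

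The cost is a short addition to each of three notes, and source and time fields if the case report forms lack them. The downside is a few more missing RV thresholds. The change stops a pre-scan number being labelled post-scan; it does not by itself detect a rise at the scan visit.

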6.5.2 Reporting of MRI Scan-Related Adverse Device Effects

An ADE or SADE related to the following should be reported as soon as possible, but no later than 10 working days, to St. Jude Medical: clotting, pulmonary embolism, or heating of the device pocket during the MRI scan. These events are likely to be associated with symptoms occurring during or immediately following the MRI scan and may manifest as chest pain, shortness of breath, or changes in vital signs during or immediately following the MRI scan.

To ensure all ADEs or SADEs related to or caused by the MRI scan are appropriately captured, before starting the scan, verbally instruct the subject to report symptoms of chest pain, shortness of breath or pocket discomfort that he/she experiences while being scanned or immediately after exiting the scanner. Note changes in vital signs such as changes in heart rate, room air blood oxygen saturation, and/or respiration rate that occur during the MRI scan that may suggest an ADE or SADE has occurred due to clotting, pulmonary embolus or related to lead tip or device pocket heating.

If symptoms during or immediately after the MRI scan suggest that an ADE or SADE has occurred due to clotting, pulmonary embolus or related to lead tip or device pocket heating, test to assess possible causes. Diagnostic testing may be performed in any order deemed appropriate by the investigator; if any test was not performed, provide medical justification for not performing that test:

- (1) A 12-lead EKG
- (2) A 2-view chest X-ray (PA and Lateral).
- (3) Room air blood oxygen saturation
- (4) A transthoracic echocardiogram.

Clinical Investigational Plan

If the subject reports pocket discomfort, ask the subject for additional descriptive information and determine if the pocket is discolored or warm to the touch. EKG, chest x-ray, room air blood oxygen saturation, or transthoracic echocardiogram testing are not required to be performed for symptoms related to device pocket heating.

Sites should report an ADE or SADE if the subject experiences a significant rise in pacing threshold ([contact] or greater) from pre-MRI scan to post-MRI scan.

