**Clinical Investigational Plan****6.0 Procedures****6.1 Study Flow Chart****Figure 1: Study Flow Chart**

**Clinical Investigational Plan****6.2 Procedures**

The study will be conducted in accordance with the CIP. All parties participating in the conduct of the study will be qualified by education, training, or experience to perform their tasks and this training will be documented appropriately.

The study will not commence until St. Jude Medical receives written approval from the IRB and relevant regulatory authorities and all required documents have been collected from the site(s).

All required study procedures at each specified interval are outlined in the section below. Refer to Table 4.

Table 4: Study Procedures and Data Collection

Procedure/Evaluation	Study Schedule			Follow-Up Visit(s) 2-12 days and/or 1 Month (-7/+ 14 days) Post MRI Scan*	
	MRI Scan Visit		Post-MRI (Same day as MRI Scan)		
	Pre- MRI	During MRI			
Informed Consent & Inclusion/Exclusion Evaluation	✓				
Medical and Surgical History	✓				
Demographic Information	✓				
Implanted SJM pacemaker, ICD, or CRT device system info.	✓				
Complete the SJM provided MRI Hazard Checklist or a site-specific checklist, per site's standard of care	✓				
Obtain device measurements (remaining battery capacity, capture threshold, sense, pacing and HVLI impedances, as applicable) at permanently programmed settings	✓		✓	✓	
Program the appropriate device settings before MRI	✓				
Monitor subject with ECG along with the site's routine monitoring**		✓			
Assess subject for adverse events		✓	✓	✓	
Program device to original settings after MRI scan			✓		
Clinical Evaluation of MRI scan			✓		
Report deviations and withdrawal	✓	✓	✓	✓	

*Refer to the study flow chart for follow-up schedule

** In cases where ECG monitoring is not readily available, monitoring via pulse oximetry alone is considered acceptable

Clinical Investigational Plan

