6.6.2 Subjects with significant parameter changes requiring multiple follow-up visits

Subjects with any of the significant parameters changes shown in Table 7 above will require multiple follow-up visits to ensure patient safety and appropriate device function. A total of 2 follow-up visits will be scheduled:

- 1) Within 2 to 12 days after the MRI scan
- 2) 1 Month (-7/+ 14 days) after the MRI scan

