6.6.5 Device Assessment during Follow-Ups

For any scheduled or unscheduled follow-up visit:

- 1) Determine the subject's underlying rhythm
 - If there is no intrinsic rhythm when the device is programmed to pace at 40 bpm, the subject is considered pacemaker dependent.
- 2) Obtain the following measurements for all leads, as applicable, with the permanently programmed parameters.
 - Remaining battery capacity
 - Capture threshold for all leads

Clinical Investigational Plan

- Sensing amplitude for RA and RV leads
- Pacing lead impedance for all leads
- HVLI impedance

NOTE: *RV capture thresholds are not required to be obtained if a high ventricular rate is present (e.g. 110bpm). If available, sites should use the automatically obtained pacing capture threshold from the most recent archival data as a substitute for the in-clinic capture threshold. RV sensing measurements are not required if the subject's intrinsic rate has been established to be ≤ 40 beats per minute.*

- 3) Evaluate the subject for adverse events (ADEs, SADEs, UADEs).

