6.8 Subject study completion

The subject's participation in this study is complete after the last scheduled follow-up per sections 6.6.2 or 6.6.3, as applicable. When the subject's participation in the clinical study has been completed the subject will return to standard medical care as per physician's recommendation.

Clinical Investigational Plan

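### The only objective rule for reporting a pacing-threshold rise reads as scan-day only; at follow-up the same rise is reported only on investigator judgement

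*Combined protocol and SAP*

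**What the plan says.** **Reporting rule.** Section 6.5.2, under Post-MRI Scan Procedures, asks sites to report an ADE or SADE for a pacing-threshold rise of a given size "or greater) from pre-MRI scan to post-MRI scan". The size is not legible in the text available for review, which is not a fault of the plan.

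**Meaning of post-MRI.** Table 4 (section 6.2) labels the stage "Post-MRI (Same day as MRI Scan" and gives follow-up visits a separate column. Section 6.6 bases the follow-up schedule on the "change in the device parameters from the MRI Scan Visit (pre-MRI scan to post-MRI scan measurements".

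**Table 7.** Section 6.6.1 lists significant parameter changes, among them "Increase in capture threshold" of at least 0.5 V. These decide how many follow-up visits a subject has. They are not event definitions.

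**Follow-up.** Subjects with a Table 7 change have a visit "Within 2 to 12 days after the MRI scan" and another at 1 month (6.6.2). All others have the 1-month visit only (6.6.3). Section 6.6.5 repeats the capture, sensing and impedance measurements at any follow-up visit and then says "Evaluate the subject for adverse events (ADEs, SADEs, UADEs". It states no numeric limit and no value to compare with. Under 6.8, "participation in this study is complete after the last scheduled follow-up".

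**General safety rules.** The ADE definition in 8.1.2 has no time limit and no numeric limit. Section 8.3 runs safety reporting through the follow-up visits and covers ADEs of any seriousness. Section 8.3.2 makes ADEs reportable whether or not they are linked to the scan.

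**The concern.** Table 1 (section 3.3) lists damage from heated lead electrodes, with capture or sensing lost, as a risk of the scan, and sets no time limit on it. Repeat device measurements at follow-up are the plan's means of seeing such an effect late. Yet the one rule that turns a measured rise into a reportable event appears to be tied to the scan day.

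What is at stake is the consistency of the ADE summary, a named output in sections 4.4.2 and 12.1.3. If a rise is an event by rule on one day and by local opinion on another, the summary partly reflects when and where the rise was measured. A rise that a site does not call an ADE also does not reach the events committee (14.1), the event rates that the Steering Committee watches (14.2), or follow-up to resolution (8.3.2).

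The point concerns the measurement-based reporting rule. It does not concern the definition of an MRI-related complication in 8.2.2 or the primary endpoints.

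**Working it through.** The plan gives no figure for this point, so the check sets its sections side by side.

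1. **Is the 6.5.2 rule tied to the scan day?** Section 6.5.2 does not say so itself. Three things point that way: it sits in section 6.5, Table 4 and the synopsis label that stage as same-day, and section 6.6 uses the same pre-to-post phrase for measurements at the MRI Scan Visit. The reading is inferred, but it is the natural one.

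2. **Does another rule cover follow-up?**
   - Table 7 is applied to the scan-day change and sets visits only.
   - Section 6.6.5 measures, then asks for an event evaluation, without a limit or comparator.
   - Section 8.2 covers capture of scan-related ADEs but sends sites back to 6.5.2.
   - Section 8.1.2 defines an ADE as a device-related adverse event. Section 8.1 does not define an adverse event, so it does not settle whether a symptomless threshold rise is one.

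3. **Same rise, different day.** Take a rise that just meets the 6.5.2 limit.

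| Measurement at which the rise is first seen | Numeric rule | Route to an ADE report |
|---|---|---|
| Same-day post-scan | 6.5.2 | By rule |
| 2-12 day visit (only after a scan-day Table 7 change) | None | Investigator judgement (6.6.5, 8.1.2, 8.3, 8.3.2) |
| 1-month visit | None | Investigator judgement (same sections) |

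4. **Who is exposed?** All subjects are due a 1-month visit. Taking a month as 30 days, the window is 30 − 7 = day 23 to 30 + 14 = day 44. For subjects without a scan-day Table 7 change this is the only scheduled follow-up. An unscheduled visit is defined in 6.6.4 by an ADE, SADE or UADE, so a silent rise does not itself lead to one. With up to 100 centers (4.2), unguided judgement can vary.

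5. **How many subjects?** The documents give no rate of late rises. For scale only, each 1% of subjects is 0.01 × 300 = 3 in total, or 0.01 × 150 = 1.5 per device group. How many of these sites would report on judgement is unknown.

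**The case against.** The strongest reply is that the general rules already cover late rises. Events must be evaluated at every follow-up visit, directly after the threshold is measured. The ADE definition has no time limit, reporting runs through follow-up, and only the transient events of Table 2 are exempt (8.3.1). This stands. A reader might infer from 6.5.2 that a rise first found at 1 month falls outside event reporting altogether, so that it need not be reported, adjudicated or followed. The documents do not support that. Once the investigator judges the rise to be an ADE, 8.3 and 8.3.2 require reporting and monitoring until it resolves, and 14.1 has it adjudicated. The end of scheduled participation in 6.8 does not cancel these duties.

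Three further replies have some force:

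- **The same-day reading is inferred.** True. The plan elsewhere calls the later visits post-MRI follow-up. If the broader meaning was intended, the fix only makes it explicit.
- **Follow-up measurements are summarized (12.1.3).** True, so late changes are not hidden. But the section does not promise change from the pre-scan value or a count of subjects beyond a limit, and a group summary can mask a few large individual rises.
- **Forms and the committee charter are kept separately.** They may contain prompts. They cannot be checked here.

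A reader might also want to attach a confidence limit to a count of zero late events. That would assume that no site reports any late rise. Pooling all 300 subjects would also cut across the by-group summary in 12.1.3. The plan specifies no confidence limit for ADEs, and none should be quoted for this point.

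**Conclusion.** The concern holds in a limited form. The plan has one objective threshold-rise reporting rule. In context it compares pre-scan with same-day post-scan values, and no equivalent is stated for follow-up. A late rise is reportable, but only through investigator judgement. Identical measurements can therefore be classified differently by visit and by site, which can under-count late changes in the ADE summary.

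The size cannot be estimated from the documents. The conclusion rests on the same-day reading of 6.5.2 and on the forms and charter not already supplying a follow-up criterion. This is a worthwhile, inexpensive improvement to a secondary safety output in a descriptive registry without a hypothesis (12.9). It does not threaten the primary results.

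**What to change.** - **Sections 6.5.2 and 6.6.5.** Reconcile them so that the existing 6.5.2 limit is compared with the pre-MRI value at every later study measurement: same day, 2-12 day, 1-month and unscheduled. Leave relatedness to the investigator and the events committee. No new cut-off is proposed. If a scan-day-only rule is intended, say so and state how later rises are classified.
- **Section 12.1.3.** Tabulate, by device group and visit, the number and percentage of subjects whose change from the pre-MRI value meets each existing Table 7 limit. Use as denominator the subjects with both measurements, since some thresholds need not be obtained. Note that the 2-12 day column is a selected group, because only subjects with a scan-day change are scheduled for that visit.

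The cost is a sentence in each of two sections and one table. The measurements are already collected, and the visit schedule and clinical management do not change. The drawback is a few more reports, some reflecting ordinary variation that a study without a control group cannot separate from a scan effect. Adjudication and the descriptive table help to put these in context.
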